1. LIST OF ABBREVIATIONS

ACT	Artemisinin Combination Therapy
CDC	Centers for Disease Control and Prevention
COMREC	College of Medicine Research Ethics Committee
CRF	Case Report Form
CSP	Circumsporozoite protein
DBS	Dried Blood Spot
DMC	Data Management Core
EIR	Entomologic Inoculation Rate
ELISA	Enzyme-Linked Immunosorbent Assay
EPI	Expanded Programme on Immunization
F1 mosquitoes	First generation mosquito progeny
GCP	Good Clinical Practice
GPS	Global Positioning System
HC	Health Center (or Centre)
HH	Household
HIV	Human Immunodeficiency Virus
HLC	Human Landing Catch
ICF	Informed Consent Form
ICH	International Conference on Harmonization
IEC	Independent or Institutional Ethics Committee
IRB	Institutional Review Board
ITN	Insecticide-Treated Net
LLIN	Long-Lasting Insecticide-Treated Net
LC50	Single dose that kills 50% of test mosquitos
MoH	Ministry of Health
MOP	Manual of Procedures
mRDTs	Malaria rapid diagnostic tests
NMCP	National Malaria Control Programme

ICEMR	International Center for Excellence in Malaria Research
ITNs	Insecticide-treated bed nets
MDHS	Malawi Demographic and Health Survey
MSU	Michigan State University
NCST	National Commission for Science and Technology
NIAID	National Institute of Allergy and Infectious Diseases
NIH	National Institutes of Health
OPD	Outpatient Department
PBO nets	Piperonyl butoxide-impregnated nets
PCR	Polymerase Chain Reaction
PI	Principal Investigator
PID	Participant Identification Number
RTS,S	Central repeat region of Plasmodium falciparum circumsporozoite protein (CSP); T-cell epitopes of the CSP; and the hepatitis B surface antigen (HBsAg).
SAE	Serious Adverse Event
SES	Socio-Economic Status
SMC	Safety Monitoring Committee
SOP	Standard Operating Procedure
SP	Sulfadoxine-Pyrimethamine
SSA	Sub-Saharan Africa
WBC	White Blood Cell
WHO	World Health Organization

2. EXECUTIVE SUMMARY

Introduction: The decline in malaria incidence has stalled globally and incidence is increasing in some high transmission settings of sub-Saharan Africa (SSA), including Malawi. The situation is worsening despite the scale-up of previously effective interventions, raising concerns that the impact of current malaria control and prevention strategies maybe compromised.

Problem: There is an urgent need for innovative approaches to malaria control and Malawi is currently positioned to assess two of the most promising new interventions. The Malawi Ministry of Health (MOH) is launching large scale projects to evaluate a new formulation of insecticide-treated bed nets with a chemical synergist, piperonyl butoxide (PBO), designed to enhance the insecticidal effect of pyrethroids and the new malaria vaccine RTS,S/ ASO1 (RTS,S). In an effort to gain the most information from these, interventions Malawi's National Malaria Control Programme (NMCP) have invited the Malawi International Center for Excellence in Malaria Research (ICEMR) to evaluate the effectiveness of the two interventions (alone and in combination) on malaria prevalence and transmission.

Objective: In this proposed implementation study, we propose to assess the impact of PBO nets and RTS,S vaccine on *Plasmodium* infection prevalence and transmission.

Study type and methodology: We will enroll children in a prospective cohort study in which the follow-up will be at the 2nd, 4th, and 6th month. Using malaria Rapid Diagnostic Tests (mRDTs), all participants will be screened for malaria infection at enrollment. Participants with positive mRDTs will will be treated with a full, weight appropriate treatment course of dispersible artemether-lumefantrine (LA) by government staff. The mRDTs and treatment of mRDT positive children will be repeated at the final visit. Similarly, all participants will be examined for hemoglobin levels at enrollment and at every two-month follow-up visits using Hemoglobin Color Scale (HCS). Children in households that are scheduled to receive both PBO nets and RTS,S vaccine will be compared to children in households that are not scheduled to receive either of these interventions. The outcomes of interest will be malaria infection prevalence, gametocyte prevalence and entomological evidence of the force of infection.

Results dissemination: Results from this study will be shared with malaria national programs in Malawi and globally, through conference presentations and peer-reviewedpublications, to contribute to the development of policy in rolling out these new interventions.

3. BACKGROUND INFORMATION

3.1 Significance of the problem

Malaria remains a significant global health problem, with an estimated 216 million cases worldwide in 2016 (WHO, 2017). At present, the main approaches to malaria control are insecticide-treated bed nets (ITNs) and prompt diagnosis with effective treatment. Malaria-related morbidity and mortality declined globally over the past decade, however, this progress has stagnated. Indeed, five million more malaria cases occurred globally in 2016 than in 2015, with the greatest increases occurring in countries like Malawi (WHO, 2017). This increased incidence arose despite continued use of previously effective interventions, raising fears about the future usefulness of current malaria control activities, and highlights the urgent need for innovative approaches to malaria control. In Malawi, two new interventions will be introduced over the period of surveillance supported by the Malawi International Center of Excellence in Malaria Research (ICEMR): a new formulation of bed nets that is designed to manage insecticide resistance and a pilot study of RTS,S/AS01 vaccination in young children. The Malawi ICEMR has a truly unique opportunity to evaluate the implementation and impact on *Plasmodium* transmission of these two interventions.

Implementation and interactions of RTS,S and bed nets: Both the RTS,S vaccine and PBO nets have been studied as part of large clinical trials. RTS,S vaccine has been evaluated in the setting of high ITN use (Agnandji, 2011) and PBO nets have been studied with and without indoor residual spraying. Impacts of these interventions, when implemented on a large-scale programmatic level, must be evaluated for their individual and combined effects, and their cost-effectiveness against other potential interventions. The combined effects of these interventions could be enhanced or diminished by interactions. For example, if young children receiving the RTS,S vaccine are also from households more likely to use ITNs, then vaccine effectiveness could be relatively more. Or it may be that parents of those receiving malaria vaccine believe their children have become protected against malaria illness, and therefore become less vigilant in shielding their children from mosquito bites. Perhaps people's perceptions of PBO nets (benefits over conventional nets or concerns about the added synergist) will alter their use compared to conventional ITNs. The significance of our study lies in our ICEMR's ability to evaluate both of these major new interventions, and systematically collect evidence about the impact of RTS,S vaccination and PBO nets on the incidence of *Plasmodium* infection.

3.2 Novel interventions to prevent malaria

The use of piperonyl butoxide (PBO) nets: Pyrethroids are the only class of insecticide approved for use in ITNs, but resistance among the *Anopheles* vectors in Africa is widespread. In Malawi, pyrethroid resistance is present in the two major malaria vectors, *An. funestus* and *An. arabiensis*, and has recently become more severe (Mzilahowa, 2016). Increased prevalence and intensity of pyrethroid resistance is a key contributor to the observed failure of current ITNs to protect against *Plasmodium* infection in our setting and elsewhere. We recently demonstrated that pyrethroid-based ITNs in southern Malawi provided only modest or no protection against infection and disease (Mathanga, 2015; Buchwald, 2017) yet no alternative insecticide is currently available. However, the addition of a chemical synergist, piperonyl butoxide (PBO), is designed to enhance the insecticidal effect of pyrethroids even in the face of resistance. PBO inhibits the enzyme that detoxifies the pyrethroid, allowing the pyrethroid to act on the mosquito. A recent cluster-randomized trial in Tanzania showed that use of PBO nets compared to conventional pyrethroid nets produced 44% and 33% protective efficacy in the first and second year, respectively. The impact of PBO net use was also detectable in key entomological measures

including *Anopheles* density, sporozoite rate and entomological inoculate rates (Protopopoff, 2018). Following these promising preliminary results, Malawi's National Malaria Control Program (NMCP) will lead a PBO-net mass distribution campaign in six districts, presenting us with the opportunity to study the effectiveness of these nets in the context of real-world program setting. The significance of this opportunity lies in our ability to carefully evaluate the impact on *Plasmodium* transmission and also investigate accompanying changes in pyrethroid resistance to better understand the mechanism of protection.

3.3 Malaria vaccine

A highly effective malaria vaccine remains elusive, but the RTS,S vaccine has progressed through the clinical development stages. RTS,S is a subunit vaccine that includes a portion of the circumsporozoite protein (CSP) co-expressed with Hepatitis B surface antigen combined with AS01 adjuvant. The Phase 3 trial of three doses administered to 5-17-month-olds confirmed moderate protection, with overall efficacy estimates of 50.4% against clinical malaria and 34.8% against severe malaria after three doses (Agnandji, 2011). Efficacy, which waned over time, was marginally improved by boosting at 18 months. The European Medicines Agency adopted a positive scientific opinion of the vaccine for use outside of the European Union. The WHO has created the Malaria Vaccine Implementation Program (MVIP) and selected Malawi as one of the sites to explore the feasibility, efficacy and safety of RTS,S vaccination in the context of routine use. In addition, when exploring RTS,S feasibility and safety in routine health delivery, little evidence exists regarding how RTS,S vaccine may affect *Plasmodium* infection and transmission. An analysis of several RTS,S trials suggested 70-90% protection against microscopy-defined infection (Penny, 2015), but this does not consider submicroscopic, PCR-detected *Plasmodium* infections containing gametocytes infectious to mosquitoes. The significance of our proposed studies is that RTS,S vaccination may reduce human infection prevalence and transmission to mosquitoes. Thus, RTS,S vaccine may offer indirect protection and decrease infection in other age groups. Alternatively, if vaccination permits low-density *Plasmodium* infections that do not lead to disease and treatment-seeking, vaccinees may actually serve as sources of added household transmission. The Malawi Ministry of Health (MOH) has invited our ICEMR to help analyze impacts of RTS,S vaccination on *Plasmodium* transmission and malaria incidence. Knowledge of these outcomes is critical to future role out of the vaccine.

3.4 Malaria in Malawi

Malaria remains a major public health problem in Malawi. Recent surveys suggest that malaria infection risk exists throughout Malawi, with the highest risk being along the hotter, wetter and more humid low-lying regions, and the lowest in the highland areas (Kazembe, 2007). Despite the scale-up of ITNs in certain locations, there has been no corresponding reduction in malaria risk and morbidity (Roca-Feltrer, 2012; Okiro, 2013; Sisya, 2015). From 2000 to 2010, the number of people living in hyper-endemic conditions actually increased by 37% (MOH-KEMRI, 2013) whilst the number of reported cases of malaria increased from 3.7 million in 2005 to 6.8 million in 2010, an increase of 46% in a population that grew by 14.1% during the same time period. Malaria morbidity burden also remained high in hospital settings (Okiro, 2013). Further, the incidence of malaria ranged from 200 - 600 cases per 1,000 populations per district in 2013, with 9.2 million courses of artemisinin combined treatment (ACT) dispensed in 2013 alone. Yet during this time frame, the proportion of under-five children and pregnant women who slept under an ITN the previous night reportedly increased from 25% and 8% to 67% and 62%, respectively, by 2013. Although few data reflecting actual transmission exist, these numbers suggest that the intensity of *P. falciparum* transmission may actually have increased despite a decade of intensified nationwide investment in malaria control and prevention.

3.5 Preliminary Studies

Evaluation of effectiveness of large-scale bed net projects. Beginning in the early 2000s and continuing into the current decade, we analyzed the effectiveness of ITN (Lindblade, 2015; Mathanga, 2015) programs in Malawi. In a 2012 study, the incidence of infection with *P. falciparum* was 30% lower in ITN users than non-users despite the presence of pyrethroid resistance in the *An. funestus* population (Lindblade, 2015). In parallel, there was no reduction in cases of malaria in children presenting with fever to clinics who used bed nets compared to matched controls not using ITNs, suggesting no effect of bed net use in contrast to a previous systematic review that showed reductions of 50-62% in malaria episodes across different transmission settings (Mathanga, 2015), highlighting the need for more effective interventions across different transmission intensities.

Insecticide resistance in Malawi. In support of the government campaigns to roll out ITNs, we coupled analyses of insecticide resistance in vector populations to *describe what the IR analyses were coupled to* (Mzilahowa, 2008; Riveron, 2015). Results revealed a spectrum of phenotypic and genotypic resistance attributes and in particular, showed that many populations of *An. funestus* were resistant to presently used pyrethroids used in ITNs in Malawi. We have shown that mortality rates realized by exposing wild-caught *Anopheles* to seven different ITN types, including two dually-treated nets (Olyset plus and PermaNet 3.0) were very low, indicating that the *An. funestus* strains were resistant (Fig. 1). Mortality of mosquitoes was complete (100%) only when they were exposed to the top-panel of PermaNet 3.0, which was treated with high doses of deltamethrin and piperonyl butoxide (PBO), a synergist. This study provides an opportunity to measure the impact of PBO nets at the population level in an area of differing insecticide resistance levels and in the context of other interventions.

4. JUSTIFICATION

Despite massive scale-up of malaria control interventions in Malawi, especially ITNs, malaria disease burden still remains high. This study will assess the impact of two new interventions being introduced into the Malawi national malaria control program. The outstanding research question is

a) What is the impact of RSS,S vaccine on *P. falciparum* prevalence and transmission?

The focus of past RTS,S clinical trials has always been the protective efficacy against clinical disease. Given the large-scale cluster-randomized introductions of the vaccines, and the existing ICEMR community-based surveillance infrastructure, we will evaluate the effect of RTS,S vaccination on the prevalence of *P. falciparum* infection in the vaccinated children and their household members and also on various measures of transmission. This critical information has never previously been explored in evaluating malaria vaccine effectiveness. In addition, the use of serological markers will generate measures of transmission for individuals on a finer scale than entomological measures alone and will allow controlling for exposure level in the analysis. Accurate estimations of effectiveness in prior vaccination studies have been hampered by the lack of measures of individual exposure.

[figure not shown]

Figure 1. Mortality of *An. funestus* exposed to seven LLIN types was <40% except to PermaNet 3.0.

b) Does the use of PBO nets decrease exposure to malaria infection and limit transmission? Although PBO nets are likely to have more potent insecticide activity, only one study has been published to date that shows that the implementation of PBO nets decreases human malaria infection (Protopopoff 2018).

c) What are the combined effects of RTS,S vaccine and PBO nets?

While it is possible that the impact of RTS,S vaccine plus the impact of PBO nets is additive, human behavior, parasite dynamics and vector responses may lead to either synergistic or antagonistic effects when they are combined. The factorial study design proposed in this application allows the evaluation of the impact and interaction of these two interventions.

Findings from this study will have implications for policy makers since understanding both the direct and indirect, population-level benefits of malaria vaccination and PBO nets will be critical when countries decide whether to adopt these intensive interventions. Hence the data obtained in this study will be used to enhance program effectiveness, both at national and international level. This study will be divided into two phases. This protocol is particularly focused on detailing the first phase of the study, although it briefly summarizes the proposal of the second phase of the study.

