5 OBJECTIVES

5.1 Broad Objective

To assess the combined impact of RTS,S (malaria) vaccination and PBO nets on *Plasmodium* infection and transmission, and how they interact when they are introduced together.

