5.2 Specific Objectives

The specific objectives for the study are as follows:

1. To estimate the impacts of PBO nets and RTS,S vaccine on the prevalence and transmission of *Plasmodium* infection. (Phase 1).
2. To assess the feasibility of evaluating the impact of RTS,S vaccine and PBO nets on the prevalence and transmission of *Plasmodium* infection in a larger scale study. (Phase 2).

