6 METHODS

6.1 Study Design

This will be a prospective cohort study. This is a preliminary study to determine if we can detect an impact of RTS,S vaccine combined with PBO nets on parasitological, entomological and/or serological evidence of infection and transmission. If this preliminary study yields significant results, we will have the opportunity to apply for funding from our sponsor (US National Institutes of Health) for a much larger study that will assess the impact of each of these interventions individually and how they interact with each other. If we are approved to conduct this multi-arm study, we will submit a new protocol to COMREC and the MSU IRB for review and approval.

Using malaria and vaccine registers, we will establish community-based cohorts of children age-eligible to receive RTS,S vaccination from the two extreme groups: i.e. Nyambi health centre in Machinga and Kalembo health centre in Balaka. The Machinga district, is undergoing implementation of both RTS,S vaccination and PBO nets (RTS,S and PBO interventions). Balaka households do not receive RTS,S vaccination and only receive conventional nets arms (Table 1). We will enroll children of the age that would be eligible for vaccination and all of the children over nineteen months and under ten years of age in their house. We will conduct interviews and collect specimens at enrolment and at 2, 4 and 6 months, as described below. During these visits, data on individual, household, social, and behavioral determinants, immunization status, ITN use will be collected.

Table 1: Overview of study design and methods

Specific Objective 1: To estimate the impact of PBO nets and RTS,S vaccine on Plasmodium infection prevalence and transmission in Malawi.		
Methods	Data sources	Key variables/ outcome

Phase 1: Recruited from Nyambi Machinga health centre – in catchment areas that receive RTS,S vaccination and PBO nets.
 
Recruited from Kalembo health centre in Balaka – in catchment areas that receive conventional nets and no malaria vaccination.
	
Interviews of parent/guardians participantsBlood samplesCaptured mosquitosHuman reporting about NetsFinger prick blood specimens	
Plasmodium falciparum infectionGametocyte presenceAnopheles spp. abundanceAnopheles gravidityAnopheles sporozoite rateNet usageImmunization statusSerological markers

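### Phase 1 enrols only the both and neither groups, so the factorial claim, the separate impacts and the interaction in the objectives cannot be delivered

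*Combined protocol and SAP*

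**What the plan says.** Section 4 poses three questions: (a) the impact of the vaccine, (b) whether PBO nets reduce exposure and transmission, and (c) the combined effects of the two. Under (c) it raises possible synergy or antagonism and concludes: "The factorial study design proposed in this application allows the evaluation of the impact and interaction of these two interventions".

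The broad objective in section 5.1 covers the combined impact "and how they interact when they are introduced together". Specific Objective 1 in section 5.2, labelled Phase 1, is "To estimate the impacts of PBO nets and RTS,S vaccine on the prevalence and transmission" of infection. The Phase 2 objective beside it concerns only whether a larger evaluation would be feasible.

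The operative sections describe something narrower. Section 6.1 draws its cohorts "from the two extreme groups": Nyambi health centre in Machinga (RTS,S and PBO nets) and Kalembo health centre in Balaka (conventional nets, no RTS,S). The executive summary states the same comparison, section 6.4 recruits for it, and section 6.3.2 powers only the combination against none. Section 6.1 calls the study preliminary. It leaves each intervention's own impact and their interaction to a larger multi-arm study, which depends on significant results and funding and would have a new protocol.

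**The concern.** A factorial design needs all four combinations of vaccine and net type. Phase 1 has the two corners and neither single-intervention cell. A property that section 4 claims for the design is therefore absent, and part of what sections 5.1 and 5.2 set as objectives cannot be met with any sample size or model.

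What is at stake is interpretation. Section 4 says the findings should inform policy makers deciding whether to adopt these interventions. With the objectives as they stand, a difference between Nyambi and Kalembo could be reported as evidence for the vaccine, for PBO nets, or about how they interact. The data separate none of these.

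**Working it through.** **1. The plan's own figure.** Inputs from section 6.3.2, children aged 7-18 months: 25 clusters of 20 per arm (500), control risk 21% (30% high season, 20% low), within-cluster correlation (ICC) 0.004 (0.05 high, 0.00 low), 80% power, two-sided 0.05. Effective size per arm is 500 / (1 + 19 × ICC), entered in a two-proportion power calculation.

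| | Effective n per arm | Detectable effectiveness | Plan states | Power at the stated value |
|---|---|---|---|---|
| Overall | 500/1.076 = 464.7 | 33.2% | 34% | 81.9% |
| High season | 500/1.95 = 256.4 | 35.5% | 36% | 81.2% |
| Low season | 500/1 = 500 | 33.0% | 33% | 80.0% |

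The cluster-trial formula, with 0 to 2 clusters added per arm, gives 33.0-34.3% overall. The stated figures reproduce, and they refer to both versus neither only.

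**2. What two cells identify.** Let v = 1 for RTS,S and b = 1 for PBO nets, with log risk = β0 + β1·v + β2·b + β3·v·b.

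- Kalembo (v = 0, b = 0): β0
- Nyambi (v = 1, b = 1): β0 + β1 + β2 + β3
- Difference: β1 + β2 + β3

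The design matrix has rank 2 for 4 parameters. A check of each quantity finds β1, β2 and β3 not estimable and their sum estimable. Setting β3 = 0 leaves rank 2 for 3 parameters, so the two main effects still cannot be separated. All four cells would give rank 4, with every term estimable.

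**3. What this means for one result (illustration).** The 34% detectable effect is a combined risk ratio of 1 − 0.34 = 0.66. The implied interaction ratio is 0.66 / (RR vaccine × RR nets). The single-intervention ratios below are assumptions.

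| RR vaccine alone | RR nets alone | Interaction ratio | Reading |
|---|---|---|---|
| 1.00 | 0.66 | 1.00 | Nets only |
| 0.66 | 1.00 | 1.00 | Vaccine only |
| 0.80 | 0.825 | 1.00 | Both, no interaction |
| 0.66 | 0.66 | 1.52 | Both, antagonism |
| 1.00 | 1.00 | 0.66 | Effect only in combination |

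If the vaccine ratio may lie in 0.50-1.00 and the net ratio in 0.56-1.00, the interaction ratio may be anywhere from 0.66 (0.66/1.00) to 2.36 (0.66/0.28).

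**4. District.** Each arm is one health centre in one district, so a district term δ adds to the contrast, which becomes β1 + β2 + β3 + δ. The districts differed beforehand: section 6.2 gives 2015 incidence of 367 per 1,000 in Machinga and 310 in Balaka, a ratio of 367/310 = 1.18.

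**5. Whether other cells are sampled.** Section 6.2 describes RTS,S and control clusters in both districts, so areas with only one intervention were expected to exist. None is enrolled.

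**The case against.** The best defence is that the operative text is already right. The executive summary and section 6.3.2 frame Phase 1 as combined versus none, and section 6.1 expressly defers separate effects and interaction. Section 4 adds that the study has two phases and that this protocol mainly details the first. The factorial sentence and the unphased broad objective can then be read as describing the whole programme. This largely stands: a reader might infer that the investigators overlooked the limit, and section 6.1 shows that they did not. It does not remove the conflict. Objective 1 is labelled Phase 1, the Phase 2 objective is feasibility, and the multi-arm study is conditional, so the objectives nowhere move the separate effects or the interaction out of Phase 1.

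A second defence is that the data hold more than two group means. Section 6.4 records RTS,S doses and net type for each child, and section 6.5 compares children who do and do not comply with each intervention. Enrolled older children are outside the protocol's vaccine-eligible ages, so their contrast reflects mainly nets plus any indirect vaccine effect. These comparisons may be informative, but they do not replace the missing cells. The compliance groups are self-selected and compared at baseline to look for confounding and selection, and section 6.4 seeks Nyambi households where children have already received both interventions. The older children's contrast still mixes nets, indirect vaccine effect and district.

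Three stronger readings are not supported:

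- That question (c) goes wholly unanswered. As worded it asks about combined effects, which the two cells address; only the synergy or antagonism part fails.
- That the net effect would by itself explain the plan's target, because section 3.2 cites 33% second-year efficacy for PBO nets against the 34% here. The 34% is a detectable effect, not an expected one, and section 3.2 gives neither outcome nor scale for the 33%.
- That the sponsor intends to credit one component. No section says so.

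**Conclusion.** The point holds as a mismatch between the claims in sections 4, 5.1 and 5.2 and the two-group design of Phase 1. One contrast is available where three effects are named. Questions (a) and (b) and the synergy or antagonism part of (c) cannot be answered, while the combined-effect part of (c) can be addressed subject to confounding with district. The non-identifiability follows from the enrolled groups alone and needs no numerical assumption. The risk-ratio decompositions rest on assumed single-intervention effects and only illustrate it. The sample size for the combined contrast is not in question.

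**What to change.** - Restate section 5.1 and Objective 1 in section 5.2 as the both-versus-neither contrast between the Nyambi and Kalembo catchment areas. Naming the catchment areas keeps the district limitation visible.
- Delete the factorial sentence in section 4, or assign it to the later multi-arm study described in section 6.1. Mark questions (a), (b) and the synergy or antagonism part of (c) as questions for that study.
- Align the Phase 2 objective in section 5.2 with section 6.1, so that it is clear which phase or protocol will estimate separate effects and interaction.
- State in section 6.5 that Phase 1 results will not be attributed to either intervention alone or to their interaction.

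The cost is wording and narrower claims; the 500 children per arm and the 34% detectable effect do not change. Enrolling the two missing cells is a much larger step and would not readily settle interaction. With 500 per cell, 21% risk, ICC 0.004 and a joint ratio of 0.66 split equally (cell risks 0.21, 0.171, 0.171 and 0.139, effective n 464.7), the standard error of the log interaction ratio is √Σ[(1 − p)/(n·p)] = 0.206. The ratio detectable at 80% power is then exp(±2.80 × 0.206), about 0.56 or 1.78, so only a large interaction would show.
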